#### **ABBREVIATIONS**

8-OHdG	8-hydroxy-deoxyguanosine
AE	Adverse Event/Experience

AT As-treated

BBB Blood Brain Barrier
BID Twice per day
BL Baseline

BMI Body Mass Index
BP Blood Pressure

C Celsius

CBC Complete Blood Count
CCC Clinical Coordinating Center
CDE Common Data Element
CHD Coronary Heart Disease

Chem Chemistry

CI Confidence Interval
CNS Central Nervous System
CRF Case Report Form
CSF Cerebrospinal Fluid

CTCC Clinical Trials Coordinating Center

CVD Cardiovascular Disease DAT Dopamine Transporter

DATATOP Deprenyl and Tocopherol Antioxidative Therapy of Parkinson's Disease

DBP Diastolic Blood Pressure
DCC Data Coordinating Center
DS1 DAT scan 1 (screening)
DS2 DAT scan 2 (optional)

DSMB Data and Safety Monitoring Board

dL Deciliter

ECG Electrocardiogram

eCRF Electronic Case Report Form eDC Electronic Data Capture eDE Electronic Data Entry

FDA Food and Drug Administration

FRAP Ferric Reducing Antioxidant Power (or Ferric Reducing Ability of Plasma)

GCP Good Clinical Practice

GDS-S Geriatric Depression Scale – Short version

GFR Glomerular Filtration Rate

HDFP Hypertension Detection and Follow-up Program

HDPE High-density polyethylene

HIPAA Health Insurance Portability and Accountability Act

HPFS Health Professionals Follow-up Study

HR Hazard Ratio

Hr Hour

ICH International Conference on Harmonization

ID Identification

IEC Independent Ethics Committee

IMP Inosine monophosphate (a.k.a. inosinic acid or inosinate)

IND Investigational New Drug
IRB Institutional Review Board

K Potassium kg Kilogram

LFT Liver Function Test
MAO Monoamine Oxidase

MCID Minimum clinically important difference
MDS-UPDRS Movement Disorders Society UPDRS
MedDRA Medical Dictionary for Regulatory Activities

mEq Milliequivalent mITT Modified Intent-to-treat

mL Milliliter

MMSE Mini-Mental State Examination MoCA Montreal Cognitive Assessment

MRFIT Multiple Risk Factors Intervention Trial

MS Multiple Sclerosis

NET-PD National Institutes of Health Exploratory Trials in PD

NHS Nurses Health Study

NIH National Institutes of Health

NINDS National Institute of Neurological Disorders and Stroke

OTC Over-the-counter PD Parkinson('s) disease

PDQ-39 Parkinson's Disease Questionnaire – 39 item version

pH 'power of Hydrogen' (negative log of hydrogen ion concentration)

PK Pharmacokinetics
PAU Persistently acidic urine
PI Principal Investigator

PO By mouth

PRECEPT Parkinson Research Examination of CEP-1347 Trial

PRO Patient-reported outcome
PSG Parkinson Study Group
PW Premature Withdrawal
QA Quality Assurance
QC Quality Control
QID Four times per day
QoL Quality of Life

RBD REM (Rapid Eye Movement) Behavior Disorder

SBP Systolic Blood Pressure

S&E ADL Schwab and England Activities of Daily Living Scale

SAE Serious Adverse Event/Experience

SAP Statistical Analysis Plan SC Steering Committee SC1 (SC2) Screening Visit 1 (or 2) SD Standard Deviation Smart4SURE Smartphone substudy and app for the SURE-PD3 trial SPECT Single Photon Emission Computerized Tomography

SU Serum urate

SURE-PD Safety of URate Elevation in Parkinson's Disease

SURE-PD3 Study of URate Elevation in Parkinson's Disease, phase 3

SV Safety Visit (at month 27)

SWEDD Scans Without Evidence of Dopaminergic Deficit

TE1 (or TE2) Telephone Evaluation 1 (or 2)

TID Three times per day

TSH Thyroid-Stimulating Hormone (thyrotropin)

UAC Uric acid crystalluria

UPDRS Unified Parkinson's Disease Rating Scale

VS Vital Signs

#### **SYNOPSIS**

**Study Title:** A randomized, double-blind, placebo-controlled trial of urate-elevating inosine treatment to slow clinical decline in early Parkinson's disease

**Study Acronym:** SURE-PD3 (Study of URate Elevation in Parkinson's Disease, phase 3)

#### **Study Objectives**

**Primary** – To determine whether oral inosine dosed to moderately elevate serum urate (from ≤5.7 mg/dL to 7.1-8.0 mg/dL) over 2 years slows clinical decline in early PD.

## **Secondary** – To determine:

[figure not shown]
- a) safety and tolerability of urate-elevating inosine treatment,
- b) short-term (3 mo) wash-in and wash-out effects on MDS-UPDRS and other outcomes,
- c) time to disability warranting dopaminergic medication, and
- d) long-term (2 yr  $\pm$ 3 mo of wash-out) effects on:
  - i) need for initiating dopaminergic medication changes,
  - ii) specific non-motor measures of cognitive, mood and autonomic function (vital signs and orthostatic changes), and
  - iii) quality of life and functional disability measures.

### **Design and Outcomes**

Multicenter, randomized, double-blind, placebo-controlled trial with clinical decline assessed as change in the primary outcome variable of the Movement Disorders Society-Unified Parkinson's Disease Rating Scale (MDS-UPDRS), a composite scale comprising patient- and clinician-reported outcomes.

Secondary outcome variables include safety, disability warranting initiation of dopaminergic therapy, quality of life and functional disability measures, and specific non-motor measures of cognition, mood and autonomic function.

#### **Diagram of Timeline & Treatment**

#### **Interventions, Evaluations and Duration**

Capsules containing 500 mg of inosine (active drug) or lactose (placebo) will be taken orally up to two capsules three times per day (i.e., up to 3 gm/day) for 24 months. In the inosine-treated group the number of capsules taken per day will be titrated to serum urate levels – measured at trough at all study visits (V's in the above diagram) no more than three months apart – in order to achieve concentrations of 7.1-8.0 mg/dL. Initial dosing will be tailored to individualized factors including gender and pretreatment serum urate, and then advanced gradually toward the projected target dose. Adjustments in dosing of placebo capsules in the control arm will be algorithm-based to match dosing of inosine capsules in the active drug arm.

Following study drug discontinuation all subjects will be followed during a 3-month wash-out period (w/o) by telephone calls (T's in the above diagram) and a final study visit. All study visits after screening will include measurement of the primary outcome variable (MDS-UPDRS) and most will include secondary outcome variables: adverse events, dose adjustments, disability warranting initiation of dopaminergic therapy, Quality of Life in Neurological Disorders (Neuro-QOL), 39-item Parkinson's Disease Questionnaire (PDQ-39), Schwab & England Activities of Daily Living (S&E ADL) scale, Montreal Cognitive Assessment (MoCA), and orthostatic vital signs.

## **Study Population**

To enroll ~270 subjects with early PD (not yet requiring treatment with levodopa or dopamine agonist) and with lower serum urate, ~667 people diagnosed with probable early PD will be consented at ~60 US Parkinson Study Group (PSG) clinical sites. Initial screening for serum urate levels at or below 5.7 mg/dL (approximate population median) and other clinical eligibility criteria (e.g., to exclude those at high risk of adverse effects of urate elevation) will identify 300 probable candidates. They will undergo neuroimaging of dopamine transporter (DAT) ligand binding uptake to enhance diagnostic confidence by excluding ~10% who have scans without evidence of dopaminergic deficit (SWEDDs). The resultant cohort of ~270 subjects with lower serum urate predictive of more rapid clinical progression will be well suited to study whether urate-elevating inosine treatment can slow clinical progression in early PD.

#### Sample Size

Power for the primary outcome of rate of change in MDS-UPDRS over 24 months is based on a random slopes model with shared baseline. The model will include fixed effects of time, treatment x time, gender, gender x time, baseline MAO-B inhibitor use, and baseline MAO-B inhibitor use x time and random siteand subject-specific intercepts and slopes. Use of a shared baseline adjusts for baseline MDS-UPDRS score in addition to the adjustment for gender and baseline MAO-B inhibitor use. Other baseline covariates may be included in the final model based on any revision in our understanding of predictors of PD progression prior to finalizing the analysis plan and breaking the blind. MDS-UPDRS assessments completed after a subject has initiated dopaminergic therapy will be censored. Based on applying the same primary analysis model to data from SURE-PD, the following variance components were estimated for MDS-UPDRS trajectories (assuming a 1.29x conversion factor from UPDRS scores): site-level variance (intercept = 12.6, slope = 0.0159 / month, covariance = -0.446), subject-level variance (intercept = 99.8, slope = 0.297 / month, covariance = 3.70), and residual variance = 17.9. Similarly informed by experience in SURE-PD we assumed that 70% of subjects would initiate dopaminergic therapy plus up to 8% additional loss to follow-up prior to initiating dopaminergic therapy. With quarterly follow-up for MDS-UPDRS, the variance and censoring estimates above, a final two-sided test at alpha = 0.046, allowing for two non-binding interim analyses at one-sided alpha = 0.001 each, the study would have 80% power with n = 270 subjects randomized 1:1 to placebo or urate elevation if the true effect of treatment were to reduce 2-year increase in MDS-UPDRS by 6.3 points, a 20% reduction in the expected rate of progression. This is robust to variable gender-specific enrollment rates and treatment efficacy as long as the average effect of treatment across genders in the ratio enrolled is 6.3 points over 2 years.

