## 10.3 Sample Size and Accrual

## 10.3.1 Effect Size

The effect size for determining power is based on estimates of the minimum clinically important difference (MCID) for changes in MDS-UPDRS I-III total scores and on the previously observed association between baseline serum urate levels and the rate of change in UPDRS I-III total scores in the DATATOP, PRECEPT, and SURE-PD trials.

Hauser et al. report that placebo-treated subjects who reported being minimally worse over 26 weeks on a global impression of change assessment experienced an average increase in UPDRS I-III total scores of 4.9 units. Given our expectation that elevated serum urate will delay progression, not improve symptoms, a MCID related to minimal worsening among placebo subjects seems most appropriate in this context. Based on estimates by Goetz and colleagues for PD patients with mild symptoms (Hoehn and Yahr stage I/II), MDS-UPDRS I-III total scores are roughly 30% larger than UPDRS I-III

total scores (2.5x for 16 questions in Part 1, 1.1x for 52 questions in Part II, and 1.2x for 108 questions in Part III, yielding a weighted conversion of 1.29x), implying a MCID of 6.3 MDS-UPDRS I-III total score units.

We expect to enroll subjects with mean baseline serum urate of approximately 4.5 mg/dL based on data from SURE-PD and then raise levels in the active arm 3 mg/dL on average at trough sampling. A 3 mg/dL difference in baseline serum urate predicted 8.1 and 2.1 unit per year differences in UPDRS I-III total score slopes in the DATATOP and PRECEPT trials. In the SURE-PD trial, subjects randomized to moderate serum urate elevation (7 to 8 mg/dL at random sampling) progressed 1.1 unit / year slower than placebo arm subjects with wide confidence bounds (95% CI 4.8 units / year slower to 2.8 units / year faster). Note that this estimate from SURE-PD (see Fig. 7D) is conservative relative to an alternative model for the effect of serum urate elevation (see Fig. 7C).

[figure not shown]

Figure 13. Meta-analysis of the rate of UPDRS change in early PD subjects with lower serum urate. Early, largely untreated PD subjects with a serum urate of <5.9 mg/dL at baseline from DATATOP (n=155; double-placebo only), PRECEPT (n=446) and SURE-PD (n=25; placebo only) were followed for up to two years. The overall UPDRS rate was obtained by weighting each estimate by the inverse of its standard error.

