## 10.3.2 Sample Size

Power for the primary outcome of rate of change in MDS-UPDRS I-III total score is based on a random slopes model with shared baseline. The model will include fixed effects of time, treatment x time, gender, gender x time, an indicator of baseline MAO-B inhibitor use, and baseline MAO-B inhibitor use x time and random site- and subject-specific intercepts and slopes, each with unstructured covariance. MDS-UPDRS assessments completed after a subject has initiated dopaminergic therapy will be censored.

Based on applying the same primary analysis model to data from SURE-PD, the following variance components were estimated for UPDRS I-III total scores: site-level variance (intercept = 9.75, slope = 0.0123 / month, covariance = -0.346), subject-level variance (intercept = 77.4, slope = 0.230 / month, covariance =2.87), and residual variance = 13.9. We assume that 70% of subjects will initiate dopaminergic therapy based on experience in SURE-PD plus up to 8% additional lost to follow-up prior to initiating dopaminergic therapy. With the planned schedule for MDS-UPDRS assessments (screening, baseline, 3 weeks, 6 weeks, 12 weeks, and then quarterly through 24 months), the variance and censoring estimates above imply an effective standard deviation for UPDRS I-III total score slopes of 0.587 units / month or 0.758 units / month on the scale of MDS-UPDRS I-III total scores.

Given a standard deviation of 0.76 units / month, a final two-sided test at alpha = 0.046 allowing conservatively for two interim analyses at alpha = 0.001 each, the study would have 80% power with n = 270 subjects randomized 1:1 to placebo or urate elevation if the true effect of treatment were to reduce the rate of increase in MDS-UPDRS I-III total score by 6.3 points over 2 years.

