Given preliminary data from SURE-PD on the variance components from random-slope models for MoCA after Rasch score conversion and S&E ADL, the effective standard deviations (in points per month) for these measures given our planned follow-up schedule are 0.038 and 0.31, respectively. Weaver et al. report an among-person standard deviation for PDQ-39 at 24 months after deep brain stimulation of 14.2 to 15.3. Assuming conservatively no within-person covariance, that would imply a standard deviation for 24-month change of approximately 30. Given these estimates, the trial will have 80% power to detect 2-year treatment differences on these outcomes as small as 0.31, 2.5, and 10.3, respectively.

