## 10.4.5 Efficacy or Futility

Interim analyses for efficacy or futility will be performed by the unblinded statistician after 2000 and 5000 person-months of period 1 follow-up are completed, roughly one-third and three-quarters of total anticipated period 1 follow-up. Non-binding early stopping for efficacy will be proposed if the active treatment group is superior to placebo for the primary efficacy outcome based on a one-sided p-value of 0.001 or less. Other criteria used in deciding whether to stop early for efficacy will include evaluation of safety and secondary efficacy outcomes. We propose stringent early stopping criteria for efficacy in order to ensure that evidence for efficacy is unambiguous if the study is stopped early. Non-binding early stopping for futility will be proposed based on a beta-spending rule quadratic in information time. If there were no benefit from treatment, then the trial would have a 51% probability of early stopping for futility based on this rule. As with the efficacy evaluation, the decision to stop early for futility will also include

evaluation of feasibility, safety, and secondary efficacy outcomes. Because the efficacy and futility stopping rules are non-binding, we conservatively assume that each look is cumulative for alpha and ignore possible findings of futility when calculating the overall type I error.

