3.8 Sample Size

urate. Early, largely untreated PD subjects with a serum urate of <5.9 mg/dL at baseline from DATATOP (n=155; double-placebo only), PRECEPT (n=446) and SURE-PD (n=25; placebo only) were followed for up to two years. The overall UPDRS rate was obtained by weighting each estimate by the inverse of its standard error.

Power for the primary outcome of rate of change in MDS-UPDRS I-III total score is based on a random slopes model with shared baseline. The model will include fixed effects of time, treatment x time, sex, sex x time, an indicator of baseline MAO-B inhibitor use, and baseline MAO-B inhibitor use x time and random site- and subject-specific intercepts and slopes, each with unstructured covariance. MDS-UPDRS assessments completed after a subject has initiated dopaminergic therapy will be censored.

Based on applying the same primary analysis model to data from SURE-PD, the following variance components were estimated for UPDRS I-III total scores: site-level variance (intercept = 9.75, slope = 0.0123 / month, covariance = -0.346), subject-level variance (intercept = 77.4, slope = 0.230 / month, covariance =2.87), and residual variance = 13.9. We assume that 70% of subjects will initiate dopaminergic therapy based on experience in SURE-PD plus up to 8% additional lost to follow-up prior to initiating dopaminergic therapy. With the planned schedule for MDS-UPDRS assessments (screening, baseline, 3 weeks, 6 weeks, 12 weeks, and then

quarterly through 24 months), the variance and censoring estimates above imply an effective standard deviation for UPDRS I-III total score slopes of 0.587 units / month or 0.758 units / month on the scale of MDS-UPDRS I-III total scores.¹²

Given a standard deviation of 0.76 units / month, a final two-sided test at alpha = 0.046 allowing conservatively for two interim analyses at alpha = 0.001 each, the study would have 80% power with n = 270 subjects randomized 1:1 to placebo or urate elevation if the true effect of treatment were to reduce the rate of increase in MDS-UPDRS I-III total score by 6.3 points over 2 years.

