Given preliminary data from SURE-PD on the variance components from random-slope models for MoCA after Rasch score conversion, GDS-15, and S&E ADL, the effective standard deviations (in points per month) for these measures given our planned follow-up schedule are 0.038, 0.097, and 0.31, respectively. Weaver et al.¹³ report an among-person standard deviation for PDQ-39 at 24 months after deep brain stimulation of 14.2 to 15.3. Assuming conservatively no within-person covariance, that would imply a standard deviation for 24-month change of approximately 30. Given these estimates, the trial will have 80% power to detect 2-year treatment differences on these outcomes as small as 0.31, 0.80, 2.5, and 10.3, respectively.

4. Baseline Characteristics, Study Endpoints, and Final Disposition

4.1 **Baseline Characteristics**

Each analysis sample will be summarized overall and by treatment group for the following characteristics: randomization site; age, sex, race, ethnicity, time since symptom onset, time since PD diagnosis, modified Hoehn and Yahr score, resting tremor, use of an MAO-B inhibitor, serum urate, MDS-UPDRS scores, NeuroQoL module scores, years of education, MMSE, MOCA score, PDQ-39 score, modified Schwab and England ADL score, smoking history, caffeine consumption, sense of smell, RBD history, vigorous physical activity, serum urate, DAT ligand uptake, BMI, supine systolic and diastolic blood pressure, and orthostatic hypotension.

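### Two planning figures do not follow from the plan's own inputs: the synopsis variance components (scaled by 1.29 instead of 1.29²) and the PDQ-39 change SD (about 30 instead of about 21); N = 270 and 80% primary power stand

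*Protocol*

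**What the plan says.** **Variance components.** The Protocol Synopsis (Sample Size) reports components for MDS-UPDRS trajectories estimated from the phase 2 trial, "assuming a 1.29x conversion factor from UPDRS scores". The site-level values are 12.6 (intercept), 0.0159 (slope) and -0.446 (covariance). The others are "subject-level variance (intercept = 99.8, slope = 0.297 / month, covariance = 3.70), and residual variance = 17.9". The paragraph then attributes 80% power at n = 270 to these variance estimates and the censoring assumptions.

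Protocol 10.3.2 and SAP 3.8 give the same components on the original UPDRS scale: site 9.75 / 0.0123 / -0.346, "subject-level variance (intercept = 77.4, slope = 0.230 / month", subject covariance 2.87 and residual 13.9. They report effective SDs for "slopes of 0.587 units / month or 0.758 units / month" on the UPDRS and MDS-UPDRS scales respectively, round the latter to 0.76, and base the power statement on that.

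Protocol 10.3.1 and SAP 3.7 show what 1.29 means. It converts an MCID of 4.9 UPDRS points, "yielding a weighted conversion of 1.29x), implying a MCID of 6.3 MDS-UPDRS I-III total score units".

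**PDQ-39.** Protocol 10.3.3 and SAP 3.9 cite an among-person SD of 14.2 to 15.3 at one time point and continue: "Assuming conservatively no within-person covariance, that would imply a standard deviation for 24-month change of approximately 30". The SAP then lists detectable two-year differences for MoCA, GDS-15, Schwab and England ADL and PDQ-39 "as small as 0.31, 0.80, 2.5, and 10.3, respectively". The protocol lists the same values without GDS-15.

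**The concern.** If scores are multiplied by 1.29, their SD is multiplied by 1.29 and their variances and covariances by 1.29². The synopsis appears to have applied the factor once to quantities that need it squared. The printed inputs then do not support the power quoted beside them, and the protocol holds two incompatible sets of planning variances. This matters mainly as a benchmark. Protocol 10.4.4 compares interim precision with the original planning assumptions, and SAP 6.4, which drops formal re-estimation, still has variance components reviewed on blinded data. Correctly planned data judged against the synopsis values would look noisier than planned.

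For PDQ-39, zero covariance means that the variance of a change is the sum of two variances, so the SD grows by √2. A value of 30 is about twice the single-time SD. The plan would then understate its own sensitivity on this outcome.

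**Working it through.** **1. The plan's primary power.** Inputs (Protocol 10.3.2, SAP 3.8): slope SD 0.76 per month, effect 6.3/24 = 0.2625 points per month, two-sided alpha 0.046 (critical value 1.995), 135 per arm.

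- SE = 0.76 × √(4/270) = 0.76 × 0.1217 = 0.0925.
- Power = Φ(0.2625/0.0925 − 1.995) = Φ(0.842) = 80.0%.

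The stated 80% at N = 270 reproduces. With the unrounded SD of 0.758 it is 80.2%.

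**2. The role of 1.29.** 4.9 × 1.29 = 6.32, the stated MCID of 6.3. Also 0.587 × 1.29 = 0.757, which agrees with the stated 0.758 to rounding. So 1.29 acts on scores and on SDs.

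**3. Synopsis values against Protocol 10.3.2.**

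| Component | 10.3.2 (UPDRS) | Synopsis | Ratio | 10.3.2 × 1.29² |
|---|---|---|---|---|
| Site intercept | 9.75 | 12.6 | 1.292 | 16.2 |
| Site slope | 0.0123 | 0.0159 | 1.293 | 0.0205 |
| Site covariance | -0.346 | -0.446 | 1.289 | -0.576 |
| Subject intercept | 77.4 | 99.8 | 1.289 | 128.8 |
| Subject slope | 0.230 | 0.297 | 1.291 | 0.383 |
| Subject covariance | 2.87 | 3.70 | 1.289 | 4.78 |
| Residual | 13.9 | 17.9 | 1.288 | 23.1 |

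All seven ratios lie between 1.288 and 1.293. The required factor is 1.29² = 1.664, so rounding does not explain the gap. The printed values are 1/1.29 = 78% of the correctly scaled ones.

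**4. What the printed values imply.** If every component is multiplied by the same constant, with visits and censoring fixed, the slope SD is multiplied by its square root: 0.587 × √1.29 = 0.667. Then SE = 0.667 × 0.1217 = 0.0812, and power = Φ(0.2625/0.0812 − 1.995) = Φ(1.24) = about 89%, against the stated 80%.

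**5. PDQ-39: the plan's detectable differences.** Formula: (1.960 + 0.842) × SD × √(4/270) = 0.341 × SD, where SD refers to two-year change (the monthly SD × 24 for the slope outcomes).

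- MoCA: 0.341 × 0.038 × 24 = 0.31 (stated 0.31).
- GDS-15: 0.341 × 0.097 × 24 = 0.79, or 0.80 with t quantiles (stated 0.80).
- Schwab and England: 0.341 × 0.31 × 24 = 2.54 (stated 2.5).
- PDQ-39 with SD 30: 0.341 × 30 = 10.2, or 10.3 with t quantiles (stated 10.3).

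One formula reproduces all four, so the question is only whether 30 is the right SD.

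**6. PDQ-39 change SD.** With equal SDs and zero covariance, SD of change = √2 × SD.

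- √2 × 14.2 = 20.1; √2 × 15.3 = 21.6.
- By contrast, 2 × 14.2 = 28.4 and 2 × 15.3 = 30.6, which brackets 30.
- Detectable difference: 0.341 × 20.1 = 6.8 to 0.341 × 21.6 = 7.4.

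**The case against.** **No operative effect.** The synopsis components enter no printed calculation outside the synopsis. The body and the SAP work from UPDRS-scale components and convert the SD properly, and the SAP governs data analysis where the documents differ. The PDQ-39 slip overstates the detectable difference, so it promises too little, and no decision depends on it. All of this stands, and it is why the point is minor. It does not make the figures right.

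**Could 1.29 be a variance factor?** Then the SD factor would be √1.29 = 1.136, the MCID would be 4.9 × 1.136 = 5.6 instead of 6.3, and the slope SD 0.667 instead of 0.758. Protocol 10.3.1 and 10.3.2 rule that out.

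**Could 30 be deliberate caution?** The stated caution is zero covariance, and that gives about 21. Reaching 30 with equal SDs requires a within-person correlation of 1 − 900/(2 × 15.3²) = −0.92 at SD 15.3. At SD 14.2 it requires 1 − 900/(2 × 14.2²) = −1.23, which is impossible. No covariance assumption compatible with the text rescues the figure.

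**Stronger readings.** A reader might infer that the trial is oversized, because the printed synopsis components would need only about 104 per arm. The documents do not support this: N rests on the SD of 0.76, which is correctly converted.

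A reader might also infer that the 51% probability of futility stopping under no benefit (Protocol 10.4.5, SAP 6.5) is a third error. The documents say only: "Non-binding early stopping for futility will be proposed based on a beta-spending rule quadratic in information time". They give rough fractions of follow-up, but no total beta and no information fractions. Assuming total beta 0.20 and looks at information 1/3 and 3/4, the null stopping probability would be about 89%, but those inputs are assumptions. The DSMB Charter, which is not among the documents reviewed, may or may not hold the boundaries. The 51% is not shown to be wrong; at most it is a question for the sponsor.

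**Conclusion.** Two stated planning figures are wrong on the plan's own inputs; severity minor.

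- **Synopsis components:** understated by a factor of 1.29. They imply a slope SD of about 0.667 and about 89% power, in conflict with the 80% in the same paragraph. The 0.667 assumes the same visit and censoring pattern that produced 0.587. The error is confined to the Protocol Synopsis.
- **PDQ-39:** the change SD is 20.1 to 21.6, not about 30, and the detectable difference is about 7 (6.8 to 7.4), not 10.3. This assumes equal SDs at the two times and the zero covariance that the text states. The error is in both documents and is conservative.

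The primary sample size of 270, its 80% power, the type I error and the primary analysis are unaffected.

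**What to change.** In the Protocol Synopsis, restate the MDS-UPDRS components as site 16.2 / 0.0205 / -0.576, subject 128.8 / 0.383 / 4.78 and residual 23.1, leaving N and power as they are. Alternatively, quote the UPDRS-scale components from 10.3.2, labelled as such, with the converted SD of 0.758.

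In Protocol 10.3.3 and SAP 3.9, restate the PDQ-39 change SD as about 21 and the detectable two-year difference as about 7 (6.8 to 7.4).

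The cost is wording only. Nothing changes in sample size, analysis model, alpha, interim rules or data collection.
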